## **9.4 STATISTICAL ANALYSES**

### **9.4.1 General Approach**

The response rate will be determined and reported along with a 95% confidence interval. Other time-to-event outcomes will be reported using Kaplan-Meier curves.

### **9.4.2 Analysis of the Primary Endpoints**

The ORR in each cohort will be determined and reported along with a 95% confidence interval.

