### Design:

- Phase 2 study of patients with relapsed and refractory GZL and extranodal DLBCL
- Patients will be treated with pembrolizumab 200 mg (flat dose) IV every 3 weeks provided they have clinical benefit and no unacceptable toxicity; patients who achieve a complete response (CR) will have the option stop after 1 year of therapy.
- All responding patients (CR, PR, or SD with clinical benefit) who subsequently relapse or progress within 1 year after discontinuation of study drug are eligible for re-treatment.
- At least 20 evaluable patients each with GZL and DLBCL will be evaluated on this protocol for the primary endpoint (overall accrual ceiling of 52 patients)

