## **9.2 SAMPLE SIZE DETERMINATION**

The trial will be conducted in two cohorts using a single stage design for evaluating efficacy in each cohort since modestly high clinical response rates are expected in both cohorts.

In the GZL cohort, results from a prior study indicate that 3 of 3 patients had a complete response when treated with (authors data, manuscript accepted for publication). With 20 evaluable patients, there would be 91% power to rule out 50% and be consistent with 80% who may be able to experience a clinical response, using an exact binomial test with a 0.10 one-sided significance level. As an illustration, if 20 evaluable patients are enrolled, 14 of 20 (70.0%) who experience a clinical response would have an associated one-sided lower 90% confidence interval bound of 53.3%, and simultaneously an associated one-sided upper 90% confidence interval bound of 83.4%. This demonstrates that 14 responses in 20 patients would be a desirable result based on the parameters selected.

In the PCNSL and extranodal DLBCL cohort, newly published results in 5 patients suggest the overall response rate will be moderately high. With 20 evaluable patients, there would be 88% power to rule out 40% and be consistent with 70% who may be able to experience a clinical response, using an exact binomial test with a 0.10 one-sided significance level. As an illustration, if 20 evaluable patients are enrolled, 12 of 20 (60.0%) who experience a clinical response would have an associated one-sided lower 90% confidence interval bound of 43.3%, and simultaneously an associated one-sided upper 90% confidence interval bound of 75.1%. This demonstrates that 12 responses in 20 patients would be a desirable result based on the parameters selected.

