Within the PCNSL and extranodal DLBCL cohort, the goal will be to enroll a total of 10 PCNSL patients and 10 extranodal DLBCL patients. By doing so, at the conclusion of the trial, there will potentially be adequate patients to make an approximate estimate of the response rate for each group, which could provide information that may guide future development in these patient subsets. While 20 patients may be needed for evaluation per cohort, in order to allow for a small number of inevaluable patients, we intend to initiate treatment in 48 eligible subjects. In order to also account for ineligible patients (i.e., screen failures who do not initiate treatment), the accrual ceiling will be set at 52 patients. If 18-20 patients may be accrued onto this trial per year, accrual should be completed within 2 to 2.5 years.

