#### 11.2 PARTICIPATION OF CHILDREN

The original intent was for the study to include participation of children. Specifically, that subjects who are at least 14 years old will be included because mediastinal gray zone lymphomas do occasionally affect younger age subjects and because there is no adequate treatment at this time. The age cut-off is based on the rarity of this disease in younger children.

However, given the difficulty in recruitment and decision to close the study to accrue early, and that no children were enrolled to the study prior to the decision to close, children were ultimately not included. Due to required protocol updates at the request of the NIH IRBO (made in early 2021), the study was revised to note enrollment and inclusion of only adults in the study.

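### Does reporting ORR with a 95% confidence interval in section 9.4 undo the one-sided 0.10 exact test that section 9.2 powers?

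*Combined protocol and SAP*

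**What the plan says.** Section 9.2 plans a single-stage evaluation in each cohort with 20 evaluable patients, "using an exact binomial test with a 0.10 one-sided significance level". For GZL the rate to exclude is 50%, the target is 80% and the stated power is 91%. For PCNSL and extranodal DLBCL the figures are 40%, 70% and 88%. Each cohort has a worked illustration with one-sided 90% bounds: 53.3% and 83.4% at 14/20, and 43.3% and 75.1% at 12/20. The text concludes "This demonstrates that 14 responses in 20 patients would be a desirable result based on the parameters selected" and "This demonstrates that 12 responses in 20 patients would be a desirable result based on the parameters selected".

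The analysis sections are shorter. Section 9.4.1 has "The response rate will be determined and reported along with a 95% confidence interval", and 9.4.2 has "The ORR in each cohort will be determined and reported along with a 95% confidence interval". Neither repeats the test, the null rates or the 0.10 level, and neither says whether the interval is descriptive. Section 9.1 is headed as the statistical hypothesis but lists only endpoints.

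Three other places bear on the evaluable number. The Précis plans "At least 20 evaluable patients each with GZL and DLBCL will be evaluated on this protocol for the primary endpoint". Section 9.2 adds "we intend to initiate treatment in 48 eligible subjects". Section 11.2 reports that children were not included, "given the difficulty in recruitment and decision to close the study to accrue early".

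**The concern.** Read alone, 9.4.2 specifies the primary analysis as an interval whose level differs from that of the test used to size the trial. A two-sided 95% interval has 2.5% in each tail, while the design test uses 10% in one tail. A result can therefore pass the test while the interval still covers the null rate, and this happens at exactly the two counts that 9.2 presents as good outcomes.

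If someone judged success by whether the 95% interval clears the null, the hurdle would rise by one response in each cohort and the stated power would no longer apply. The illustrations are for 20 patients only. With early closure the evaluable number may differ, and no success count is listed for any other size. In an open-label study, an unstated rule also raises the worry that a reading could be picked after the responses are known.

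**Working it through.** **Inputs (all from 9.2).** n = 20 per cohort; exact binomial test; one-sided level 0.10; null and target rates 0.50 and 0.80 (GZL), 0.40 and 0.70 (extranodal DLBCL).

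**Formulas.** For r or more responses, P(X ≥ r | p) = Σ C(n,k) p^k (1−p)^(n−k), summed over k = r to n. The critical count is the smallest r with P(X ≥ r | null) ≤ 0.10. Power is the same sum at the target rate. An exact (Clopper-Pearson) lower bound with tail area a exceeds the null rate when P(X ≥ x | null) < a. So the one-sided 90% bound uses a = 0.10, and the two-sided 95% interval uses a = 0.025.

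**Step 1: reproduce the plan's figures.**

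| Cohort | r | P(X ≥ r, null) | Power |
|---|---|---|---|
| GZL | 13 | 0.1316 | not admissible |
| GZL | 14 | 0.0577 | 0.9133 |
| Extranodal | 11 | 0.1275 | not admissible |
| Extranodal | 12 | 0.0565 | 0.8867 |

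The critical counts are 14 and 12, the same as the illustrations. Power is 91.3% against a stated 91%, and 88.7% against a stated 88%. The second would round to 89%, which is immaterial. The one-sided 90% bounds come out at 53.3% and 83.4% for 14/20, and 43.3% and 75.1% for 12/20. All four match.

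**Step 2: the 95% intervals at those counts.**
- 14/20: exact 45.7% to 88.1%, which contains 50%.
- 12/20: exact 36.1% to 80.9%, which contains 40%.
- Wilson lower limits are 48.1% and 38.7%, so the choice of interval method does not matter.

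This is what the tail areas imply: 0.0577 and 0.0565 lie between 0.025 and 0.10.

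**Step 3: where the readings part at n = 20.** The first counts whose exact 95% interval clears the null are 15/20 (lower limit 50.9%) and 13/20 (lower limit 40.8%). The readings therefore differ only at exactly 14 and exactly 12:
- GZL, true rate 80%: 0.9133 − 0.8042 = 0.1091.
- Extranodal, true rate 70%: 0.8867 − 0.7723 = 0.1144.

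If the interval decided success, power would be 80.4% and 77.2%.

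**Step 4: is the test determined at another n?** Take n = 24, half of the 48 patients to be treated (an even split is an assumption). For GZL, P(X ≥ 15 | 0.5) = 0.1537 and P(X ≥ 16 | 0.5) = 0.0758, so the critical count is 16. For extranodal DLBCL, P(X ≥ 13 | 0.4) = 0.1143 and P(X ≥ 14 | 0.4) = 0.0535, so it is 14. The same rule gives 11/15 and 9/15 at n = 15. Nothing beyond 9.2 was needed.

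**The case for a change.** The strongest case for a change is that 9.4.2 is where the primary analysis should be defined, and a reader should not have to infer the decision rule from the sample-size section. Section 9.2 calls its counts desirable rather than making them a criterion, while section 12.1 lists the primary endpoint having been met among possible grounds for closure, which presupposes a criterion. The evaluable number is also uncertain. Assuming 15 to 24 per cohort, the two readings differ at one or two counts. The power gap between them is then 8.8 points (n = 23) to 25.9 points (n = 19) in GZL, and 7.9 points (n = 24) to 35.3 points (n = 15) in extranodal DLBCL.

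Part of this stands: a pointer from 9.4.2 to 9.2 would read better. The rest carries little weight. Every power gap assumes that the 95% interval is used as a test, which no section proposes. The largest gaps also need an assumed evaluable number that the document does not give, at sizes where discreteness is least favourable. Missing success counts at other sizes leave nothing open, because null rate, level and exact test together determine them. The worry about choosing a rule afterwards is met by 9.2, which already puts the test, level and null rates in writing.

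**Conclusion.** The concern does not call for a change. The primary objective in section 1.1.1 is to determine a response rate, and a 95% interval is a conventional way to convey the precision of that estimate. An estimation interval need not share the level of the design test. Section 9.2 supplies the test for excluding 50% and 40%, and its power figures are correct for that test. Followed together, the two sections give a valid estimate beside a fully specified test, and anyone given responders over evaluable patients can carry out that test.

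At the planned 20 per cohort, the possible misreading is confined to one count in each cohort, with probability 10.9% and 11.4% at the target rates. Even there it would affect only a reader who treated the interval as the verdict. Adding a cross-reference and the word descriptive would record what an analyst would already do, and it would alter no reported result.

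This rests on two readings of the text: that 9.2 governs the test because it is the only place one is specified, and that the silence of 9.4 on the interval's role does not make it a decision rule.

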#### 9.4.3 Analysis of the Secondary Endpoints

The duration of response (DOR; beginning at the date clinical response is first identified), overall survival (OS), event free survival (EFS), and progression free survival (PFS) will be estimated for each of the two types of lymphoma individually using Kaplan-Meier curves with appropriate confidence intervals reported.

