### 6.3.5 Progression-Free Survival

Progression-free survival (PFS) is defined as the duration of time from the date of study enrollment until time of disease relapse, disease progression, or death, whichever occurs first.

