### 6.3.6 Event-Free Survival

Event-free survival (EFS) is defined as the duration of time from the date of study enrollment until time of disease relapse, disease progression, alternative therapy for lymphoma given (such as radiation), or death, whichever occurs first.

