### 6.3.7 Other

Evaluable for toxicity: All patients who receive at least 1 dose of pembrolizumab will be evaluable for toxicity.

**Evaluable for objective response:** Only those patients who have measurable or evaluable disease present at baseline, have received at least two doses of therapy, and have had their disease re-evaluated with radiographic imaging will be considered evaluable for response. These patients will have their response classified according to the definitions stated below. (NOTE: Patients who exhibit objective disease progression prior to the end of cycle 1 will also be considered evaluable.)

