## **9.3 POPULATIONS FOR ANALYSES**

All patients who receive at least 2 doses of pembrolizumab, and who have both a baseline and follow-up scan at the appropriate time to assess response will be considered evaluable and included in the analyses.

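### Section 9.3's only analysis set requires two doses and a follow-up scan; applied literally to OS, PFS and EFS, it drops early deaths and biases the curves upward whenever an excluded patient had an early event

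*Combined protocol and SAP*

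**What the plan says.** Section 9.3 (Populations for Analyses) gives one rule: "All patients who receive at least 2 doses of pembrolizumab, and who have both a baseline and follow-up scan" at a time suited to judging response "will be considered evaluable and included in the analyses". It does not say which analyses are meant.

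Section 9.4.3 states that "overall survival (OS), event free survival (EFS), and progression free survival (PFS) will be estimated for each of the two types of lymphoma individually" with Kaplan-Meier curves. It names no population, landmark or delayed-entry method.

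The clocks start earlier than the 9.3 conditions can be met. Section 6.3.5: "Progression-free survival (PFS) is defined as the duration of time from the date of study enrollment". Section 6.3.6: "Event-free survival (EFS) is defined as the duration of time from the date of study enrollment". Death is an event in both, and other lymphoma treatment is also an EFS event. OS appears in sections 1.1.2, 9.1 and 9.4.3, but section 6.3 does not define it and no start date is given.

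Section 6.3.7 gives toxicity its own set: "All patients who receive at least 1 dose of pembrolizumab will be evaluable for toxicity". For objective response it sets nearly the same two-dose and re-imaging conditions as 9.3, but adds that patients with objective progression before cycle 1 ends also count as evaluable. Section 9.3 has no such exception.

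**The concern.** To be in the 9.3 set a patient must live to a second dose and to a follow-up scan. If that set is used for a curve that starts at enrolment, membership is decided by what happens after time zero. Patients who die before the scan are never at risk in the estimate, and everyone retained is credited with the same weeks as survival. This is guarantee-time (immortal-time) bias. It is separate from who belongs in the response-rate denominator.

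Early deaths and early switches of therapy are informative events in relapsed aggressive lymphoma. The objectives in section 1.1.2 concern patients treated with pembrolizumab, not patients who were re-imaged. Curves conditional on reaching a scan do not estimate that quantity, and cannot be set fairly beside series that count everyone from enrolment or first dose.

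**Working it through.** **The plan's own figures.** The documents state no OS, PFS or EFS figure. The only design figures are for response (section 9.2), and they reproduce with 20 evaluable patients and an exact one-sided 0.10 test:

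- GZL, 50% vs 80%: reject at 14 or more of 20; exact alpha 0.0577, power 0.9133 (stated 91%).
- Extranodal DLBCL, 40% vs 70%: reject at 12 or more of 20; exact alpha 0.0565, power 0.8867 (stated 88%).

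These do not depend on the time-to-event population.

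**Guaranteed time.** Cycles last 21 days (section 3.2), so dose 2 falls at about week 3. The first scheduled scan follows cycle 2 (section 3.4.3): 2 × 21 = 42 days, or 42/30.4375 = 1.38 months. An unscheduled scan could qualify a patient sooner, so the guarantee is about 3 to 6 weeks from first dose, plus any gap between enrolment and first dose.

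**Who drops out on the literal reading.** Patients who die without a follow-up scan, and one-dose patients who stop or switch therapy, unless the 6.3.7 exception is applied to those with objective progression in cycle 1.

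**Formula.** If a curve is restricted to patients event-free at t0, it estimates S(t)/S(t0). Hence S_all(t) = S_plotted(t) × S(t0).

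**Scenario A: the plan's allowance.** Section 9.2 plans to treat 48 patients to obtain 2 × 20 = 40 evaluable, so 8 (8/48 = 16.7%) may be inevaluable. Assuming an even split, that is 4 of 24 per cohort. Let k of those 4 have an early event, and let the others share the later hazard of the retained patients. Then S(t0) = 1 − k/24.

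| k | S(t0) | plotted 80% is really | plotted 60% is really | plotted 40% is really |
|---|---|---|---|---|
| 0 | 1.000 | 80.0% | 60.0% | 40.0% |
| 1 | 0.958 | 76.7% | 57.5% | 38.3% |
| 2 | 0.917 | 73.3% | 55.0% | 36.7% |
| 4 | 0.833 | 66.7% | 50.0% | 33.3% |

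The ceiling factor is 1/0.833 = 1.20. The documents do not give k.

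**Scenario B: exponential survival, assumed medians.** With median m, S(t0) = 2^(−t0/m), and the plotted median is m + t0. For m = 6 and t0 = 1.38: S(t0) = 0.853, so 14.7% die before the scan; 6-month OS reads 0.500/0.853 = 58.6%, and the median reads 7.38 months.

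| t0 | assumed median (months) | S(t0) | 6-month OS, true → plotted | 12-month OS, true → plotted |
|---|---|---|---|---|
| 6 weeks | 3 | 0.727 | 25.0% → 34.4% | 6.2% → 8.6% |
| 6 weeks | 6 | 0.853 | 50.0% → 58.6% | 25.0% → 29.3% |
| 6 weeks | 12 | 0.923 | 70.7% → 76.6% | 50.0% → 54.1% |
| 6 weeks | 24 | 0.961 | 84.1% → 87.5% | 70.7% → 73.6% |
| 3 weeks | 6 | 0.923 | 50.0% → 54.1% | 25.0% → 27.1% |

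With t0 = 3 weeks the median shifts by 0.69 months instead of 1.38. The 3-month row implies 24 × (1 − 0.727) = 6.6 exclusions per cohort, more than the 4 the plan allows for. Scenario B fits OS. It would overstate the effect for PFS and EFS, because some early progressions in retained patients still count.

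**The case against.** The best defence is that 9.3 was written for response only. It speaks of scans timed to assess response, the Précis ties evaluable patients to the primary endpoint, and 6.3.7 nearly repeats the rule under an objective-response label. Because toxicity has its own set, 9.3 cannot govern literally every analysis. This stands as a possible reading. It does not clear the plan: 9.3 is the only population in section 9 and is not limited to response, and if it does not apply, OS, PFS and EFS have no stated population at all. The same amendment is needed either way.

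A reader might also infer that all three curves are timed from enrolment and event-free by construction in the first weeks. The documents do not support that:

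- OS has no stated origin. The bias arises from enrolment or first dose alike, but the missing definition is a separate gap.
- Only death is strictly excluded before the qualifying scan. Section 3.5.1 allows treatment past progression, so an early progressor can receive dose 2, be re-scanned and count as an event. Section 4.2 may allow radiation during treatment, and 6.3.6 counts that as an EFS event.
- The study calendar allows clinically indicated imaging and schedules imaging at end of treatment, so some early clinical failures will have a qualifying scan.
- Progression found on the week-6 scan counts in any case.

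Finally, the 8 of 48 is an allowance for inevaluability of any kind, and section 11.2 says accrual was closed early, so 48 may not have been reached.

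**Conclusion.** The point holds in conditional form. Followed as written, the plan draws OS, PFS and EFS from a set that patients enter only by surviving to a second dose and a scan. The curves are biased upward whenever at least one excluded patient had an early event. If none did, this bias is absent.

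The size cannot be derived from the documents. The 58.6% against 50% rests on exponential survival, a 6-month median and a week-6 scan. The factor of 1.20 is a ceiling that needs every planned inevaluable patient to be an early death. A reader might take either as this trial's bias; neither is. The conclusion also rests on the literal scope of 9.3, which is the plainest reading but not the only one. The affected endpoints are secondary and descriptive; response rate and power are untouched. It is still worth correcting, because the remedy is short and otherwise the population could be settled after the data are seen.

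**What to change.** In sections 9.3 and 9.4.3:

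1. Limit the two-dose, scan-based set to response, and say that toxicity uses the 6.3.7 set.
2. Estimate OS, PFS and EFS in all patients who received at least one dose, with or without a follow-up scan. A death before the first scan is an event in all three; alternative lymphoma therapy before it is an EFS event.
3. Define the OS time origin to match PFS and EFS. Requiring one dose while counting from enrolment leaves guaranteed time between enrolment and first dose; this should be small, but the plan should acknowledge it.
4. Reconcile 9.3 with the early-progression exception in 6.3.7, so that one rule decides who is evaluable for response.

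The cost is a few sentences. No new data are needed: sections 3.7, 3.7.2 and 3.7.3 already provide for collecting new therapy, disease status and survival. The downside is that the reported curves may be less favourable.

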#### 9.4.4 Safety Analyses

The type, grade and frequency of toxicities will be reported.

#### 9.4.5 Planned Interim Analyses

No interim analyses are planned because of the single stage design of the trial.

#### 9.4.6 Sub-Group Analyses

None.

#### 9.4.7 Tabulation of Individual Participant Data

None.

#### 9.4.8 Exploratory Analyses

The exploratory objectives such as seeking to identify potential biomarkers or T-cell and B-cell clones in peripheral blood which are associated with response, will be assessed using descriptive statistics as well as non-parametric methods such as exact Wilcoxon rank sum tests. The analyses will be done without formal adjustment for multiple comparisons, but in the context of the number of tests performed.

### 10 COLLABORATIVE AGREEMENTS

#### 10.1 CLINICAL TRIAL AGREEMENT

There will be a CTA between the National Cancer Institute and Merck, Inc. (CTA #01043-17) A CRADA is also being discussed and will be added in an amendment, if finalized.

### 11 HUMAN SUBJECTS PROTECTIONS

#### 11.1 RATIONALE FOR SUBJECT SELECTION

Gray-zone lymphomas (GZL) affect all races and genders, but certain subsets such as mediastinal gray-zone lymphomas occur preferentially in young adults with a slight male predominance. Extranodal DBCL and other ABC-like subtypes of DLBCL including PCNSL are more likely to occur in older patients. Across both cohorts, we anticipate an even gender distribution. This trial is directed at assessing a novel therapy using single agent pembrolizumab in patients with either previously treated GZL and patients with previously treated extranodal DLBCL. Pregnant or nursing mothers are excluded because of the potential teratogenic effects of therapy.

